#### **10.3.2. Definition of SAE**

#### An SAE is defined as any serious adverse event that

#### a. Results in death

#### b. Is life-threatening

- c. Requires inpatient hospitalization or prolongation of existing hospitalization
- d. Results in persistent or significant disability/incapacity

#### e. Is a suspected transmission of any infectious agent

#### 10.3.3. Recording and Follow-up of AE and/or SAE

#### Assessment of Intensity

#### Grade 1 (Non-Severe):

The recipient may have required medical intervention (e.g. symptomatic treatment) but lack of such would not result in permanent damage or impairment of a body function.

#### Grade 2 (Severe):

The recipient required in-patient hospitalization or prolongation of hospitalization directly attributable to the event;

and/or

the adverse event resulted in persistent or significant disability or incapacity;

or

the adverse event necessitated medical or surgical intervention to preclude permanent damage or impairment of a body function.

## Grade 3 (Life-threatening):

The recipient required major intervention following the transfusion (vasopressors, intubation, transfer to intensive care) to prevent death

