## 2.2. Background

Originating in Wuhan Province of China in late 2019, a new coronavirus named SARS-CoV-2 has spread throughout much of the world. The virus, which causes respiratory infection and in some a serious respiratory illness, was declared a pandemic by WHO in March. As of ultimo May 2020, the number of detected infected is approaching 5,5 million worldwide, and more than 350,000 people have died. In addition, the numbers of actual infected are underestimated as adequate testing in large parts of the world is impossible and a substantial number of cases are

asymptomatic. In Norway, drastic measures have achieved a controlled spread of virus, and we are currently able to treat the number of patients within the total hospital care capacity, including intensive care units. However, it must be assumed that the spread of infection will continue and that a significant number of patients will die before vaccines become available. Although most people experience mild infection, serious illness and high mortality has been observed especially among the elderly, individuals with comorbidities such as cardiovascular disease, diabetes and obesity.

As per end of May 2020, about 90% of the 235 deaths reported in Norway due to COVID-19 had occurred between patients aged 70 years or more, and 60% of all deaths occurred among patients admitted to institutions outside hospitals. Within outbreaks in care homes in Norway, case fatality rates of 15 to 50% have been reported in 2020. Patients in care homes are not prioritized for any advanced supportive medical treatment for COVID-19, and mechanical ventilation is not an option in these institutions.

The WHO has provided strategic guidelines (WHO Roadmap) for prioritization of which treatment alternatives should be systematically tested, and included convalescence plasma an alternative to consider. Norwegian hospitals are already part of the WHO Solidarity treatment trial to evaluate the safety and efficacy of antiviral treatments. Based on the potential to provide an effective COVID-19 treatment with reliably local supply until a safe and effective vaccine is available, Norwegian blood banks led by the Norwegian Health Directorate have converged on a national project for the collection and testing of convalescence plasma.

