## 5. Study Population

The target population for this study is individuals above the age of 50 in early stages of COVID-19 disease. Participants will be recruited from municipal healthcare institutions that admit and care for symptomatic COVID-19 patients in need of medical care but not referred to hospitals.

In Norway, around 15% of the population is aged 67 years or more. In 2018, around 32200 persons were living in care homes for the elderly on long term basis, and an additional 9000 persons on time-limited stays.

Data on COVID-19 in Norway showed that at end of April 2020, among the total 204 deaths in the population reported, 60% were among patients in institutions outside hospitals, and 89% of the total 204 deaths were persons aged 70 years or more (FHI.no).

The population in care homes has a high proportion of dementia and co-morbidities, which both are significant factors to take into account in the study implementation and outcome analysis. In particular, the presence of dementia represents a challenge for the consent to participate which will need to be handled by the patient's guardian if such is appointed, acting in the best interest of the patient.

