## Grade 4 (Death)

The recipient died following an adverse event

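### Grade 3 (Life-threatening) in Appendix 3 rests only on major intervention after a transfusion, so it may under-grade events managed in the care home and, read literally, cannot apply to controls

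*Protocol*

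**What the plan says.** Section 10.3.3 of the protocol grades the intensity of adverse events from 1 to 4.

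- **Grade 1 (Non-Severe)** covers events that may have needed treatment, but where "lack of such would not result in permanent damage or impairment of a body function".
- **Grade 2 (Severe)** has three alternatives. The first is admission: "The recipient required in-patient hospitalization or prolongation of hospitalization directly attributable to the event". The second is lasting or marked disability. The third applies where "the adverse event necessitated medical or surgical intervention to preclude permanent damage or impairment of a body function", with no setting named.
- **Grade 3 (Life-threatening)** has one criterion: "The recipient required major intervention following the transfusion (vasopressors, intubation, transfer to intensive care) to prevent death".
- **Grade 4 (Death)** reads "The recipient died following an adverse event".

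On the care setting, Section 2.2 says that care-home patients are not prioritised for advanced supportive treatment for COVID-19 and that "mechanical ventilation is not an option in these institutions". Section 5 recruits from institutions caring for "symptomatic COVID-19 patients in need of medical care but not referred to hospitals".

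Section 8.3 asks for intensity and causality to be assessed for AEs and SAEs. Section 10.3.2 lists being life-threatening as an SAE criterion in its own right, with no condition on treatment.

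**The concern.** A severity grade should describe what happened to the patient. Grade 3 describes what was done, or needed to be done, and all three of its examples are hospital-level care. In this population such care is less likely to be given. Two patients in the same clinical state could therefore be graded differently because one was transferred and the other was not.

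The wording also assumes a transfusion. Half of the participants are randomised to standard care alone and have none. In an open-label trial that states safety as an objective, a severity scale whose top non-fatal grade fits only one arm does not allow a like-for-like comparison of severity.

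**Working it through.** No arithmetic applies. The protocol gives no transfer rate, no expected number of severe events and no analysis by grade. The check is to take a non-fatal, life-threatening event and see where the text places it.

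**1. Under the SAE criteria (Section 10.3.2).** The event is serious because it is life-threatening. Treatment given plays no part.

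**2. Under Grade 3, with *required* read as *needed*.** If major intervention was needed to prevent death, the event is Grade 3 whether or not the intervention was given. For a transfused patient this largely agrees with step 1.

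**3. Under Grade 3, with *required* read as *received*.** The grade depends on management:

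| What happened to the surviving patient | Grade from the text |
|---|---|
| Given vasopressors, intubated or moved to intensive care | 3 |
| Treated in the care home to prevent permanent damage | 2 (third alternative) |
| Left with persistent or significant disability | 2 (second alternative) |
| Neither treated in that way, nor admitted, nor left disabled | No clear grade |

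The last row is not Grade 1 if lack of treatment would have led to permanent damage, because the Grade 1 definition excludes such an event. So under this reading an event managed in the care home is at most Grade 2, while step 1 calls it life-threatening. The same label then has two meanings within Appendix 3. The protocol does not say which reading of *required* it intends.

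**4. For a control participant.** Grade 3 needs a recipient and an intervention following the transfusion. Controls have no transfusion, so under either reading the literal text cannot be met. Two other places share the problem. Section 10.3.1 defines an AE by its timing relative to use of the study intervention, and Section 8.3.1 collects SAEs from the start of intervention. Neither says what the reference point is for a control.

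**5. Where the grade is used.** Section 8.3 has it recorded on the adverse events form, and Section 9.4 has the DMC review all safety data. The events that Section 10.1.4 lists as possible reasons to stop or pause are any death, any SAE and any adverse event of special interest. None of these refers to the grade.

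**The case against.** The strongest reply is that Grade 3 says *required*, and under a heading of Life-threatening the natural meaning is *needed*. On that reading withheld treatment does not lower the grade. This is a fair reading, but the text does not settle it, and it leaves the control-arm problem untouched.

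The second reply is that little depends on the grade. This stands in large part. A life-threatening event is an SAE whatever care is given and is reported within 24 hours (Section 8.3.1). The special-interest definitions in Appendix 4 rest largely on clinical state. Disease-related events kept out of expedited reporting are still recorded for the DMC (Section 8.3.5). The safety endpoint in Section 3 is the incidence of adverse events, not incidence by grade.

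Several stronger readings are tempting, and the protocol does not support them:

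- *A severe reaction could pass from Grade 1 to death without being graded severe.* Grade 2 is itself labelled Severe, two of its three alternatives need no hospital, and Grade 1 excludes events that would cause permanent damage if untreated.
- *Care-home patients do not get the listed interventions.* Section 2.2 speaks of priority for COVID-19 treatment and rules out only mechanical ventilation, and only in the institutions. Section 5 describes patients at recruitment. Nothing bars transfer or vasopressors for a transfusion reaction. The Synopsis leaves staff responsible for the care they judge necessary, and Section 10.3.2 foresees hospitalisation.
- *The DMC reviews rest on the grade.* Section 9.4 refers to all safety data.
- *The share of under-graded events, or a spurious ratio between arms, can be calculated.* Any such figure would only restate assumed transfer rates.

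**Conclusion.** The point holds in a narrow form. Grade 3 ties the life-threatening label to major intervention with hospital-level examples. This fits poorly with the care setting in Sections 2.2 and 5 and differs from the treatment-independent SAE criterion in Section 10.3.2. The under-grading depends on *required* being read as *received*, which the protocol leaves open. The exclusion of controls depends only on reading the wording literally.

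The consequence is limited to the severity data recorded under Section 8.3 and seen by the DMC among all safety data. Events are not lost to safety review through a wrong grade, and no stopping or pausing trigger changes. The size cannot be stated in numbers from the protocol. This is an inexpensive improvement, not a threat to the primary analysis.

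**What to change.** In Section 10.3.3, define Grade 3 as an event that put the participant at immediate risk of death, whether or not the listed interventions were given, and state that this matches the life-threatening criterion in Section 10.3.2. Write all grade definitions for a participant, and remove the reference to a recipient and to the transfusion.

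Changing the grades alone would not make the arms comparable. Align the AE definition in Section 10.3.1 and the start of SAE collection in Section 8.3.1, so that events in both arms are captured from an equivalent time point and graded alike. Add hospital transfer as a separate item on the adverse events form, so that management is recorded without being part of severity.

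The cost is a wording change in Appendix 3 and Section 8.3.1 and one more item on the form. The downside is some investigator judgement about immediate risk of death, a judgement the SAE criterion already requires. Patient care does not change.

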## Grade 4 (Death)

The recipient died following an adverse event

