# 6. Study Intervention Administered

# 6.1. Preparation/Handling/Storage/Accountability

The study intervention will be manufactured at collaborative blood bank units according to specified procedures. Briefly, potential donors of convalescent plasma will be evaluated at the blood-bank according to local SOP for plasma donors, regulated by "Blodforskriften". Male donors with previous transfusion history and all female donors will be screened for HLA I and HLA II antibodies. As a rule, plasma will be collected by apheresis in volumes of 600-850ml

dependent on body weight, and later split into therapeutic units of 200-350 ml before freezing according to local SOP. Plasma derived from a full-blood donation may also be used.

At the coordinating institution

- 1. The investigator or designee must confirm that appropriate temperature conditions have been maintained during transit for all study intervention received and any discrepancies are reported and resolved before use of the study intervention.
- 2. All study intervention must be stored in a secure, environmentally controlled, and monitored (manual or automated) area in accordance with the labeled storage conditions with access limited to the ambulatory team.
- 3. Only participants enrolled in the study may receive study intervention and only authorized site staff may supply or administer study intervention. Administration will follow SOP for transfusion. Blood pressure, pulse, respiratory frequency and temperature will be taken at pre-specified time-points (before transfusion, at the end of transfusion, 15 minutes after transfusion and 1 hour after transfusion.
- 4. Authorized site staff must monitor participants closely for 1 hour after study intervention for signs of adverse events. SAEs (Section 8.3) and other serious events (Section 8.3.5) will be reported immediately to the Medical Monitor, and an adverse events form will be recorded at the end of the study participation.
- 5. The coordinating investigator is responsible for study intervention accountability, reconciliation, and record maintenance (i.e., receipt, reconciliation, and final disposition records).

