# 8.3. Adverse Events (AEs), Serious Adverse Events (SAEs), and safety reporting

The general definitions of adverse events (AEs) and serious adverse events (SAEs) can be found in Appendix 3. Serious adverse events of special interest are described in Appendix 4: "Definitions of transfusion reactions".

AEs will be reported by the participant (or, when appropriate, by a caregiver, surrogate, or the participant's legally authorized representative).

The investigator and qualified staff at the nursing homes are responsible for detecting, documenting, and recording events that meet the definition of an AE or SAE and remain responsible for following up all AEs.

The study site will record AEs and SAEs is in the adverse events form as a part of the CRF. Both intensity and causality (related to transfusion/study intervention) of the event should be evaluated (Appendix 3).

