## 8.3.1. Frequency for Collecting AE and SAE Information

All SAEs will be collected from the start of intervention until the end of the study period (day 60). Medical occurrences that begin before the start of study intervention but after obtaining informed consent will be recorded as Medical History/Current Medical Conditions, not as AEs.

All SAEs will be recorded and reported to the medical monitor immediately and under no circumstance should this exceed 24 hours. The investigator will submit any updated SAE data to the sponsor within 24 hours of it being available.

Investigators are not obligated to actively seek information on AEs or SAEs after conclusion of the study participation. However, if the investigator learns of any SAE, including a death, at any time after a participant has been discharged from the study, and he/she considers the event to be reasonably related to the study intervention or study participation, the investigator must promptly notify the sponsor.

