## 9. Statistical Considerations

## 9.1. Statistical Hypotheses

This study is designed to detect a 40% reduction in mortality with treatment of COVID-19 with convalescent plasma among the study population, under the assumption that the mortality in the standard care group is 30%.

The primary null hypothesis is that there is no difference in mortality between standard care and standard care + treatment with convalescent plasma.

The primary alternative hypothesis is that there is a difference in mortality between standard care and standard + treatment with convalescent plasma.

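### Grade 4 on the adverse-event intensity scale is defined by sequence alone and does not require that the event led to the death

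*Protocol*

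**What the plan says.** Section 8.3 asks for two ratings of each event: "Both intensity and causality (related to transfusion/study intervention) of the event should be evaluated (Appendix 3"). The intensity scale is in Appendix 3, Section 10.3.3:

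- Grade 1 covers non-severe events, where the recipient may have needed treatment but "lack of such would not result in permanent damage or impairment of a body function".
- Grade 2 includes "The recipient required in-patient hospitalization or prolongation of hospitalization directly attributable to the event". Its disability limb also requires the disability to result from the event.
- Grade 3 covers major intervention after the transfusion to prevent death.
- Grade 4 reads, in full, "The recipient died following an adverse event".

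The fatal criterion in the SAE definition (Section 10.3.2) is "Results in death". The causality scale in Appendix 3 runs from definite to excluded and rates the event against the transfusion.

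On timing, Section 6.1 says that "an adverse events form will be recorded at the end of the study participation", the Schedule of Activities places the AE and SAE review at day 60, and Section 8.3.1 states "All SAEs will be collected from the start of intervention until the end of the study period (day 60").

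**The concern.** An intensity grade should say how severe the event was. Grade 4, taken as written, depends on whether the participant died afterwards. It sets no time window and no link from event to death, so the same mild reaction can receive a different grade according to later survival.

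Timing makes this a practical matter. If the form is completed at the end of participation, whoever grades the event may already know that the participant has died. The study population is also one in which the plan expects many deaths from COVID-19 itself.

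At stake is how far graded safety data can be trusted. The DMC reviews all safety data at 20%, 50% and 70% inclusion (Section 9.4) and recommends whether the study continues. A mild reaction certainly caused by plasma, followed by a COVID-19 death, could reach it as a Grade 4, definitely related event. Later tabulation could not recover the event's own severity if only the Grade 4 entry was kept.

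**Working it through.** **1. Does any other text supply the missing link?**

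| Item | Link required |
|---|---|
| Grade 2, hospitalisation | attributable to the event |
| Grade 2, disability | results from the event |
| SAE, fatal criterion | death results from the event |
| Causality scale | event to transfusion |
| Grade 4 | none; death comes after the event |

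Nothing in the protocol relates a death to a particular adverse event at the grading step.

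**2. One case traced through both ratings.** Mild urticaria occurs during transfusion on day 0, resolves, and is certainly due to plasma. If the participant survives, the record is Grade 1, definite. If the participant dies of COVID-19 on day 20, the Grade 4 wording is also met and the record can read Grade 4, definite. The event is identical in both.

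**3. The plan's mortality figures.** Section 9.1 designs the trial "under the assumption that the mortality in the standard care group is 30"%. Section 9.2 takes 18% in the plasma group, a hazard ratio of about 0.60, 80% power and 5% significance. Reproducing its figures:

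- Deaths (Schoenfeld, two-sided, 1:1) = 4 × (1.960 + 0.842)² / (ln 0.60)² = 120.3, rounded up to 121, as stated.
- N = 120.3 / 0.24 = 501.3, rounded up to 502, as stated (0.24 is the mean of 0.30 and 0.18).
- Inflated N = 502 × 1.008 = 506, so 253 per arm.

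Both mortality values are planning assumptions. For plasma recipients the range is 18% if the assumed effect is real and 30% if there is none.

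**4. Share of mild events affected.** Assume that a mild event and death are independent, that the event occurs on day 0, and that Grade 4 replaces Grade 1 whenever its wording is met. The share regraded by day 28 then equals 28-day mortality, 18% to 30%. Events later in follow-up have fewer days left to day 28, so their share by that day is smaller. The plan gives no separate planning figure for day 60.

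**5. Expected counts.** The protocol gives no adverse-event rate, so q, the proportion of recipients with one mild event, is an assumption. Expected count = 253 × q × mortality, with all 253 transfused.

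| q (assumed) | Recipients with a mild event | At 18% mortality | At 30% mortality |
|---|---|---|---|
| 2% | 5.1 | 0.9 | 1.5 |
| 5% | 12.7 | 2.3 | 3.8 |
| 10% | 25.3 | 4.6 | 7.6 |

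**6. Chance of at least one.** P = 1 − (1 − q × 0.18)^253 at 18% mortality:

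- q = 5%: 1 − (1 − 0.009)^253 = 90%.
- q = 10%: 1 − (1 − 0.018)^253 = 99.0%.

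**The case against.** The strongest reply is that the scale is headed as an assessment of intensity, so each grade should be read as rating the event, and an assessor may well take dying after an event to mean dying because of it. Grade 3 also uses loose sequence wording, relative to the transfusion. Moreover, a resolved mild reaction still meets Grade 1 on its own terms, and no text says that the highest applicable grade wins. CRF completion guidance is left to an SOP or Study Manual (Section 10.1.6), which may settle the matter. All of this stands, and it is why the misgrading is something that could happen, not something that must. It does not remove the defect: if the sentence supports both readings, two assessors can grade the same case 1 or 4.

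It is also true that little in the protocol turns on the grade. Adverse-event incidence is an exploratory endpoint and does not use grades (Section 3). The events that may lead to a pause include any death whatever its cause, any SAE and any event of special interest (Section 10.1.4), so a participant's death is captured without the grade. The primary endpoint comes from the death registry (Section 8.1).

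A reader might infer three stronger things that the document does not support:

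- *That many mild events would be scored as fatal.* No adverse-event rate is given, and Section 2.3 describes common transfusion risks as infrequent, though higher in the elderly. At a 2% rate the expected count is about one.
- *That 18-30% is background mortality.* These are planning values, and 18% already includes the hoped-for plasma effect.
- *That grade distributions would mirror the mortality difference between arms.* The scale speaks throughout of the recipient, and Appendix 3 ties adverse events to use of the intervention, so applying it to untransfused controls is doubtful.

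**Conclusion.** The point holds as a defect in a recording definition. Grade 4 lacks the link from event to death that the neighbouring definitions have, and the causality rating cannot stand in for it. For an event unrelated to plasma, a rating of unlikely or excluded limits false attribution to the product; for a mild reaction that plasma did cause, it gives no protection.

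The supportable size is a share: 18% to 30% of otherwise Grade 1 day-0 events in recipients could be affected by day 28. This rests on the planning mortality, on independence of mild events and death, and on the literal reading in which Grade 4 displaces Grade 1. The counts and probabilities rest further on an assumed event rate. The damage is confined to severity grading in safety reporting and in what the DMC sees. The correction is still worth making before grading starts, because it costs so little.

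**What to change.** In Appendix 3, Section 10.3.3, define Grade 4 as a death attributed to the adverse event. Add that if the participant dies of another cause, the event is graded by its own severity (Grades 1-3) and the death is recorded separately. This brings Grade 4 into line with the Grade 2 hospitalisation limb and the fatal SAE criterion.

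The cost is one sentence in Appendix 3 and the matching CRF guidance, plus an attribution assessment by the investigator for each death. Sample size, endpoints and the DMC schedule do not change.
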